## 1.6 Sample Size Estimation

The sample size is estimated to give adequate power on the two co-primary endpoints as well as for the key secondary endpoint. Sample size assumptions and determinations are summarized subsequently.

### 1) Key Secondary Endpoint – TLPP at 12 months:

- Assumptions:
  - TLPP rate through 12 months for the study device treated subjects is 55%;
  - TLPP rate through 12 months for the PTA only treated subjects is 33%;
  - Allocation ratio: 1:1;
  - Attrition (drop-out) rate (by 12 months) = 15%
  - The Type 1 error,  $\alpha = 0.025$  (one-sided); and
  - The Type 2 error,  $\beta = 0.10$  (Power =  $1 - \beta = 90\%$ ).
- Sample Size:
  - 280 randomized subjects [238 evaluable] will give 90% power with one-sided type I error = 0.025.

2) Primary Effectiveness Endpoint – TLPP at 6 months:

- Assumptions:
  - TLPP rate through 6 months for the study device treated subjects is 73%;
  - TLPP rate through 6 months for the PTA only treated subjects is 50%;
  - Allocation ratio: 1:1;
  - Attrition (drop-out) rate (by 6 months) = 10%
  - The Type 1 error,  $\alpha = 0.025$  (one-sided); and
  - The Type 2 error,  $\beta = 0.10$  (Power =  $1 - \beta = 95\%$ ).
- Sample Size:
  - 280 randomized subjects [252 evaluable] will give 95% power with one-sided type I error = 0.025.

3) Primary Safety Endpoint – Safety at 30 days:

- Assumptions:
  - The primary safety rate through 30 days in the study device treated subjects is 95%;
  - The primary safety rate through 30 days in the PTA only treated subjects is 95%;
  - Non-inferiority margin  $\delta = 10\%$ ;
  - Allocation ratio: 1:1;
  - Attrition rate (by day 30) = 5%; and
  - The Type 1 error,  $\alpha = 0.025$  (one-sided).
- Sample Size:
  - 280 randomized subjects [266 evaluable] will give 91% power with one-sided type I error = 0.025.

Hence, the sample size of 280 randomized subjects, allocated 1:1, for 140 subjects in the COVERA™ Vascular Covered Stent arm and 140 subjects in the PTA alone arm, will provide approximately 86% power for the both primary effectiveness and primary safety endpoint. The sample size of 280 randomized subjects, allocated 1:1 for 140 subjects in the COVERA™ Vascular Covered Stent arm and 140 in the PTA alone arm, will provide approximately 90% power for the key secondary endpoint.

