### 1.7.2 Primary Effectiveness Endpoint Hypothesis Test

The primary effectiveness endpoint is TLPP through 6-months. Objective: To assess if the 6 month TLPP for the COVERA™ Vascular Covered Stent is superior to that of PTA alone, by direct comparison.

The primary effectiveness endpoint will be evaluated by the following hypothesis:

**H0:** The (survival) rate  $S_1(t)$  of subjects in the study device treatment group with TLPP through  $t \leq 6$  month post index procedure is less than or equal to that  $S_2(t)$  of PTA treatment group.

**H1:** The (survival) rate  $S_1(t)$  of subjects in the study device treatment group with TLPP through  $t \leq 6$  month post index procedure is greater than that  $S_2(t)$  of PTA treatment group.

That is:

**H0:**  $S_1(t) \leq S_2(t)$ , for  $t \leq 6$  months

**H1:**  $S_1(t) > S_2(t)$ , for  $t \leq 6$  months

Rejection of the null hypothesis will signify that the 6 month TLPP of the COVERA™ Vascular Covered Stent is superior to the 6 month TLPP of PTA alone.

A Kaplan-Meier analysis will be used to estimate the survival rate of TLPP in the COVERA™ Vascular Covered Stent and PTA alone groups. A log-rank test will be used to test the primary effectiveness hypothesis to determine if COVERA™ Vascular Covered Stent is superior to PTA. The test is successful if the one-sided p-value is less than 0.025 and the result is in favor of the COVERA™ Vascular Covered Stent. In addition to the p-value of the test, the confidence intervals of the rate in each group will be provided.

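### Does the Type 2 error of 0.10 printed beside 95% power for 6-month TLPP call the sample size into question?

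*Combined protocol and SAP*

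**What the plan says.** SAP section 1.6 sets out design assumptions for three endpoints. For 6-month TLPP it assumes patency of 73% with the study device and 50% with PTA alone, 1:1 allocation, 10% attrition and one-sided alpha 0.025. It then prints "The Type 2 error, $\beta = 0.10$ (Power = $1 - \beta = 95" per cent. The sample-size line directly below reads "280 randomized subjects [252 evaluable] will give 95% power with one-sided type I error = 0.025".

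The item before it, for 12-month TLPP, prints "The Type 2 error, $\beta = 0.10$ (Power = $1 - \beta = 90" per cent, which is a consistent pair. The safety item gives no Type 2 error and states its power directly: "280 randomized subjects [266 evaluable] will give 91% power with one-sided type I error = 0.025". The section closes by saying that 280 randomized subjects "will provide approximately 86% power for the both primary effectiveness and primary safety endpoint".

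Section 1.7.2 names the analysis: "A log-rank test will be used to test the primary effectiveness hypothesis", with success at a one-sided p-value below 0.025.

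**The concern.** The Type 2 error is a stated design parameter of the primary effectiveness endpoint, and the line writes out the identity that it then breaks. Someone rebuilding the sample size from the listed assumptions meets two targets, 90% and 95% power.

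If 0.10 were the figure the designers used, the 95% would be overstated. The joint power for the two primary endpoints would then fall to about 82% if they are independent, against the 86% claimed. The chance that the trial succeeds would be lower than the plan says, so it is worth establishing which figure is wrong.

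**Working it through.** **Inputs, all from SAP section 1.6.** Patency 73% and 50% at 6 months; 1:1 allocation; 280 randomized with 10% attrition, so 280 × 0.90 = 252 evaluable, or 126 per arm; one-sided alpha 0.025 (z = 1.96); safety power 91%; joint power about 86%. The log-rank test comes from section 1.7.2. The section does not name its sample-size method, so several were tried.

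**Step 1. Reproduce the stated 95%.**

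*Two proportions, pooled z.* The mean rate is (0.73 + 0.50)/2 = 0.615.
- Standard error under the null: √(2 × 0.615 × 0.385/126) = 0.0613.
- Standard error under the alternative: √((0.73 × 0.27 + 0.50 × 0.50)/126) = 0.0596.
- Power = Φ((0.23 − 1.96 × 0.0613)/0.0596) = Φ(1.84) = 96.7%.

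*With continuity correction.* Subtracting 1/126 = 0.0079 from the difference gives Φ(1.71) = 95.6%.

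*Fisher's exact test*, by enumeration: 95.5%.

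*Log-rank*, assuming proportional hazards. HR = ln 0.73/ln 0.50 = 0.454. Expected events = 126 × (0.27 + 0.50) = 97.0, with √97.0 = 9.85.
- Freedman: Φ(9.85 × (1 − 0.454)/(1 + 0.454) − 1.96) = Φ(1.74) = 95.9%.
- Schoenfeld: Φ(9.85 × |ln 0.454|/2 − 1.96) = Φ(1.93) = 97.3%.

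The implied Type 2 error runs from 0.027 to 0.045. The stated 95% is reproduced, a little conservatively, and no method comes near 90%.

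**Step 2. The sample size each target would need** (evaluable total, with the randomized total after dividing by 0.90 in brackets):

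| Method | 90% power | 95% power |
|---|---|---|
| Pooled proportions | 184 (205) | 228 (254) |
| Continuity-corrected | 202 (225) | 244 (272) |
| Freedman log-rank | 195 (217) | 242 (269) |

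The planned 252 (280) meets the 95% target under all three methods and is well above what 90% would need.

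**Step 3. The joint power.** If the two primary endpoints are independent, joint power is the product of the two powers.
- With 95%: 0.95 × 0.91 = 0.8645, matching the stated 86%.
- With 90%: 0.90 × 0.91 = 0.819, which does not match.
- Working back: 0.86/0.91 = 0.945, so the effectiveness power behind the 86% is about 95%.

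The plan does not state independence. The lowest joint power possible under any dependence is the sum of the powers minus one: 0.95 + 0.91 − 1 = 0.86, or 0.90 + 0.91 − 1 = 0.81. By either simple rule, 86% comes from 95% and not from 90%.

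The 91% also holds up. For 95% against 95%, a 10% margin and 133 per arm, the asymptotic Farrington–Manning formula gives 91.1%, and enumerating the score test gives 92.1%.

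**Step 4. What depends on the 0.10.** In sections 1.7.2 and 1.7.4 success is decided by a one-sided p-value below 0.025; no Type 2 error enters. The 280, 252, 95% and 86% agree without it. Replacing 0.10 by 0.05 would leave every other figure and rule as it stands.

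**The case for a change.** The best case for acting is that the contradiction is real. It cannot be explained by choice of method, and the text there shows no redaction. The value that fits is determined by the plan's other figures, and correcting it would cost one digit in the sample-size justification of the primary effectiveness endpoint. All of that stands.

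Two readings that might rescue the line do not. One takes 0.10 as a planning ceiling and 95% as the power achieved, but the line sets one minus the Type 2 error equal to 95%. The other is a misread digit in text extraction, and nothing on the page suggests one.

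The objection fails on consequence. A reader is not left believing that power is 90%, because 95% appears in the same parenthesis and again in the sample-size line, and the 86% depends on it. Anyone who rebuilds the calculation from 73% and 50% with 252 evaluable subjects arrives at 95% or a little more.

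Some of the support is inferential. The rule behind the 86% is not stated, and the recomputed powers rule out 90% without fixing the Type 2 error at exactly 0.05; that value is simply the complement of the stated 95%. A carry-over of 0.10 from the 12-month item is plausible but unproven, and nothing here rests on it.

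**Conclusion.** This is a clerical slip, and no change to the plan follows. The printed 0.10 is twice the 0.05 that matches the stated power. Recomputed power is 95.5% to 97.3% at 252 evaluable, so the trial is not short of the power it claims for this endpoint, and the joint figure of about 86% is consistent with 95% and 91%.

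The conclusion rests on the plan's assumed rates and attrition, on proportional hazards for the two log-rank figures, and on either independence or the worst-case bound for the joint power. The inconsistency itself needs no assumption, since 1 − 0.10 = 0.90. Sample size, alpha, tests and success criteria are the same whichever figure is printed.

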	
the study endpoints. Note: Studies requiring extended follow-up visits for products that were investigational, but have since become commercially available, are not considered investigational studies.
 
Angiographic Exclusion Criteria
 
 
10. Additional stenotic lesions (<math>\geq 50\%</math>) in the venous outflow that are <math>> 3\text{cm}</math> from the edge of the target lesion and are not successfully treated (defined as <math>\leq 30\%</math> residual stenosis) prior to treating the target lesion.
 
11. An aneurysm or pseudoaneurysm is present within the target lesion.
 
12. The location of the target lesion would require the COVERA™ Vascular Covered Stent be deployed across the elbow joint.
 
13. The target lesion is located within a stent.
 
14. The location of the target lesion would require that the COVERA™ Vascular Covered Stent be deployed at or across the segment of fistula utilized for dialysis needle puncture (i.e., “cannulation zone”).
 
15. The location of the target lesion would require that the COVERA™ Vascular Covered Stent be placed in the central veins (subclavian, brachiocephalic, Superior Vena Cava (SVC)) or under the clavicle at the thoracic outlet.
 
16. There is incomplete expansion of an appropriately sized angioplasty balloon to its expected profile, in the operator’s judgment, during primary angioplasty at the target lesion prior to randomization.
 

Procedures:
	
All subjects will undergo a clinical evaluation at screening (prior to index procedure); treated subjects will also undergo a clinical evaluation prior to hospital discharge. A telephone screen to the subject and the dialysis center will be performed at all follow-up visits. The 6 month follow up should occur via an office visit to the investigational site in addition to the phone call to the dialysis center.

Primary Endpoints
	
Primary Effectiveness Endpoints with Hypothesis Testing
 
 
• Target Lesion Primary Patency (TLPP) through 6 months.
 
 
Primary Safety Endpoint with Hypothesis Testing
 
 
• Safety through 30 days.
 

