
Secondary Endpoints:
	
Key Secondary Endpoint with Hypothesis Testing
 
 
• TLPP through 12 months.
 
• Access Circuit Primary Patency (ACPP) through 6 months.
 
 
Secondary Endpoints without Hypothesis Testing
 
 
• TLPP through 30 days, 90 days, 18 months, and 24 months.
 
• ACPP through 30 days, 90 days, 12 months, 18 months, and 24 months.
 
• Rate of device and procedure related AEs involving the AV access circuit through 90 days, 6 months, 12 months, 18 months, and 24 months.
 
• Total Number of AV Access Circuit Reinterventions through 30 days, 90 days, 6 months, 12 months, 18 months, and 24 months.
 
• Total Number of Target Lesion Reinterventions through 30 days, 90 days, 6 months, 12 months, 18 months, and 24 months.
 
• Index of Patency Function (IPF) evaluated at 30 days, 90 days, 6 months, 12 months, 18 months, and 24 months.
 
• Index of Patency Function – Target Lesion (IPF-T) evaluated at 30 days, 90 days, 6 months, 12 months, 18 months, and 24 months.
 
• Secondary Patency evaluated through 30 days, 90 days, 6 months, 12 months, 18
 

---

	months, and 24 months. 

• Acute Technical Success.

• Acute Procedure Success (Anatomic and Clinical Success).

Lead Principal Investigator:	[REDACTED]
Angiographic Core Lab	[REDACTED]

---

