## 1.8 Evaluation of Secondary Endpoints

All secondary endpoints will be tested as exploratory only unless both primary hypotheses are successful. The testing of the secondary objectives will be performed in a hierarchical fashion in the order in which they are listed below. This means that as soon as a null hypothesis is *not rejected*, all further hypotheses will be tested for exploratory purpose only. This hierarchical testing scheme ensures that the study-wide Type 1 error rate remains at 0.05 when all of the secondary endpoints are tested at  $\alpha=0.05$ .

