#### 1.8.2 Key Secondary Endpoint with Hypothesis Test: ACPP at 6 Months

The key secondary endpoint is ACPP evaluated at 6 months (Refer to Section 4.2.1 for applicable definitions). Objective: To assess if the 6 months ACPP rates for the COVERA™ Vascular Covered Stent is superior to the primary patency rate for standard PTA, by direct comparison:

**H0:** The (survival) rate  $S_1(t)$  of subjects in the study device treatment group with ACPP through  $t \leq 6$  month post index procedure is less than or equal to that  $S_2(t)$  of PTA treatment group.

**H1:** The (survival) rate  $S_1(t)$  of subjects in the study device treatment group with ACPP through  $t \leq 6$  month post index procedure is greater than that  $S_2(t)$  of PTA treatment group.

That is:

**H0:**  $S_1(t) \leq S_2(t)$ , for  $t \leq 6$  months

**H1:**  $S_1(t) > S_2(t)$ , for  $t \leq 6$  months

Rejection of the null hypothesis will signify that the 6 month ACPP of the COVERA™ Vascular Covered Stent is superior to the 6 month ACPP of standard PTA alone.

A Kaplan-Meier analysis will be used to estimate the survival rate of ACPP in the COVERA™ Vascular Covered Stent and PTA alone groups. A log-rank test will be used to test this hypothesis to determine if the COVERA™ Vascular Covered Stent is superior to PTA alone. The test is successful if the two-sided p-value is less than 0.05 and the result is in favor of the COVERA™ Vascular Covered Stent. In addition to the p-value of the test, the confidence intervals of the rate in each group will be provided. Note that, unless both the primary endpoints, and the TLPP at 12-month endpoint are all successful, the hypothesis for the ACPP at 6-month will be tested for exploratory purpose only.

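### Does Section 1.6 claim 90% power for ACPP at 6 months, a key secondary endpoint that it never sized?

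*Combined protocol and SAP*

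**What the plan says.** Section 1.6 opens with the aim: "The sample size is estimated to give adequate power on the two co-primary endpoints as well as for the key secondary endpoint". It then sizes three endpoints.

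- **TLPP at 12 months**, headed as the key secondary endpoint: 55% versus 33%, 15% attrition, 238 evaluable, one-sided alpha 0.025, 90% power.
- **TLPP at 6 months**, primary effectiveness: 73% versus 50%, 10% attrition, 252 evaluable, 95% power.
- **Safety at 30 days**: 95% in both arms, margin 10%, 266 evaluable, 91% power.

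The closing paragraph says that 280 subjects "will provide approximately 86% power for the both primary effectiveness and primary safety endpoint" and "will provide approximately 90% power for the key secondary endpoint".

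The Protocol Summary lists a second key secondary endpoint with a hypothesis test, "Access Circuit Primary Patency (ACPP) through 6 months". SAP Section 1.8.2 begins "The key secondary endpoint is ACPP evaluated at 6 months" and specifies a log-rank test. On order, Section 1.8 states: "The testing of the secondary objectives will be performed in a hierarchical fashion in the order in which they are listed below". Section 1.8.2 makes ACPP exploratory "unless both the primary endpoints, and the TLPP at 12-month endpoint are all successful".

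**The concern.** The opening and closing sentences of Section 1.6 speak of one key secondary endpoint without naming it, and Section 1.8.2 uses the same singular label for ACPP. Read together, they could attach the 90% to a test for which the plan gives no rates, attrition or power.

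The TLPP figure cannot simply be carried over. Exclusion 10 bars subjects with other venous outflow stenoses only where these lie more than 3 cm "from the edge of the target lesion and are not successfully treated". Subjects whose other lesions were treated can enter, while the study device goes to the target lesion. Failures elsewhere in the circuit could dilute the difference between arms.

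The closing paragraph also sets a joint power (86% for both primaries) beside a stand-alone power (90%) without saying which is which, although TLPP at 12 months is confirmatory only after both primaries succeed.

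ACPP at 6 months is the only formally tested patency result for the whole circuit. If it were underpowered, a non-significant result could be misread as no benefit to the circuit.

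**Working it through.** **1. Reproduce the 90%.** Inputs from Section 1.6: p1 = 0.55, p2 = 0.33, n = 280 × 0.85 / 2 = 119 per arm, one-sided alpha 0.025.

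Power = Φ[(p1 − p2 − c − 1.96·SE0) / SE1], where c is 0, or 1/n with continuity correction.

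- SE0 = √(2 × 0.44 × 0.56 / 119) = 0.0644
- SE1 = √((0.55 × 0.45 + 0.33 × 0.67) / 119) = 0.0628
- No correction: (0.22 − 0.1261) / 0.0628 = 1.50, power 93.3%
- With correction (1/119 = 0.0084): 1.36, power 91.3%; Fisher's exact test also gives 91.3%

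The stated 90% is therefore right, slightly cautious, and takes no account of the hierarchy. It is stand-alone power for TLPP at 12 months.

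**2. Check the neighbouring figures.** The corrected formula for TLPP at 6 months (0.73 versus 0.50, 126 per arm) gives 95.6%, against 95% stated. Farrington-Manning for safety (133 per arm) gives 91.1%, against 91%. The joint figure is 0.95 × 0.91 = 86.5%, against about 86%. The type 2 error of 0.10 printed beside the 95% is a clerical slip: 1 − 0.95 = 0.05, and nothing else uses it.

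**3. Which endpoint does the 90% refer to?** Within Section 1.6 only TLPP at 12 months is headed key secondary, and its own item carries the same 90%. The enrolment row of the Protocol Summary also has a single key secondary analysis, timed at completion of 12-month follow-up. A 6-month endpoint does not fit that description. Only Section 1.8.2 uses the singular for ACPP.

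**4. Effect of the hierarchy on TLPP at 12 months.** From the stated powers, with safety independent as the plan's 86% implies:

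- All three tests independent: 0.95 × 0.91 × 0.90 = 77.8%
- 6- and 12-month statistics correlated at about 0.85 (assumed, from √(97/133) expected events): about 81%
- Perfect correlation: 0.91 × 0.90 = 81.9%

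Confirmatory success is thus about 78% to 82% on the stated figures. These are conservative for a log-rank test, because subjects who drop out still contribute earlier follow-up. A simulation at the stated rates gave about 98% for TLPP at 12 months alone and about 86% for all three tests.

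**5. Can ACPP power be judged?** Not from the documents. As an illustration, assume that ACPP is lost when TLPP is lost or when another part of the circuit fails, the latter with probability q by 6 months, equal in both arms and independent of TLPP. The ACPP rates are then 0.73(1 − q) and 0.50(1 − q). All of this is assumption; the plan gives no value for q.

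| q | ACPP rates | Two proportions, 126 per arm | Log-rank simulations, 280 randomised |
|---|---|---|---|
| 10% | 65.7% vs 45.0% | 91.5% | 93–94% |
| 20% | 58.4% vs 40.0% | 83.6% | 87–88% |
| 30% | 51.1% vs 35.0% | 73.5% | 78–80% |
| 40% | 43.8% vs 30.0% | 62.3% | 69–70% |

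The last column applies, since Section 1.8.2 specifies a log-rank test. Power is comfortable up to q of about 20%, near 80% at 30%, and lower beyond. Exclusion 10 does not fix q: it gives no frequency, and it requires those other lesions to have been treated to 30% residual stenosis or less before the target lesion.

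**The case for a change.** The best case for a change is that it would be cheap and would close a real gap. The plan claims adequacy under a label that also covers ACPP and offers nothing to support it there. The sentences most likely to be quoted are the ones that omit the endpoint's name. The bound on confirmatory success for TLPP at 12 months needs no outside rates. A sponsor with a view on ACPP rates could state the power in one line; one without could say that 280 was not sized for it.

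Much of this stands as description. The label is shared, ACPP has no stated power, and the 90% is stand-alone. What does not follow is that any planned quantity is wrong. Powering every step of a fixed sequence is good practice in some settings but not a requirement, and the hierarchy controls error whatever the power of its last step. A non-significant ACPP result would not be left without context either, because Section 1.8.2 commits to confidence intervals for the rate in each arm. Nor is ACPP the only confirmatory look beyond the target lesion: the primary safety endpoint in Sections 1.7.3 and 1.7.4 concerns events involving the access circuit and is formally tested.

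**Conclusion.** The concern does not call for a change. The shared label is loose wording that the item heading in Section 1.6 and the 12-month timing in the Protocol Summary resolve. The 90% is correct for the endpoint it was computed for (91.3% to 93.3% on recalculation). The missing ACPP power is an unstated detail about the last test in the sequence, and supplying it would leave the 280 subjects, the log-rank test, the alpha level and the order untouched.

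A reader should take the 90% as stand-alone power for TLPP at 12 months, with roughly 78% to 82% for confirmatory success on the stated powers if safety is independent. ACPP at 6 months should be read as an endpoint without a stated power, and a null result there judged by its confidence intervals. Whether ACPP is well powered remains open: about 94% to 69% for q from 10% to 40%, under assumed independent and equal failure elsewhere in the circuit. The definition of ACPP is in Section 4.2.1, which is not in the text reviewed, so that loss model is itself an assumption.
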